I will not disclose confidential information contained in this document including participant information, to anyone other than the recipient study staff and members of the IRB. I agree to ensure that this information will not be used for any purpose other than the evaluation or conduct of the clinical investigation without the prior written consent from ModernaTX, Inc. I will not disclose information regarding this clinical investigation or publish results of the investigation without authorization from ModernaTX, Inc.

The signature below provides the necessary assurance that this study will be conducted according to all stipulations of the protocol, including statements regarding confidentiality, and according to local legal and regulatory requirements, regulations, and ICH E6(R2) GCP guidelines.

Signature of Principal Investigator

Date

Printed Name of Principal Investigator

DOCUMENT HISTORY		
Document	Date	
Amendment 2	11 Dec 2023	
Amendment 1	10 Oct 2023	
Original Protocol	28 Feb 2023	

PROTOCOL AMENDMENT SUMMARY OF CHANGES

Global Amendment 2, 11 Dec 2023: Current Amendment

This amendment is considered to be substantial.

Main Rationale for the Amendment:

The main purpose of this amendment is to update the objectives and endpoints in Part B by moving immunogenicity objectives with corresponding endpoints from exploratory to primary (for noninferiority) and to secondary (for superiority). The summary of changes table describes these changes, including sections that are affected by these changes.

Section # and Name	Description of Change	Brief Rationale
Title Page, Signature Page, Protocol Amendment Summary of Changes, Header	Updated the protocol version and date, as applicable.	To reflect the current version.
Section 2.9.5.1 (Immunogenicity Analysis, Part A)	Immunogenicity analysis (paragraph 6) was changed from, "The primary analyses will be repeated using the Immunogenicity Set as a sensitivity analysis" to, "The primary analyses will be repeated using the Immunogenicity Set as a supplementary analysis".	To align with the FDA E9(R1) for Estimands.
Section 3.1 (Protocol Synopsis, Part B)	Section 3.1 (Protocol synopsis) was updated to align with changes in the relevant sections of Part B.	To align with changes in relevant sections of Part B.
Section 3.2 (Objectives and Endpoints, Part B)	 Added to primary objectives (Part B): To evaluate the humoral immunogenicity (for noninferiority) of mRNA-1010 relative to that of a licensed SD seasonal influenza vaccine (Fluarix Quadrivalent) against 4 vaccine-matched influenza virus A and B strains at Day 29 in adults 18 to <65 years old 	To align with the change to establish immunogenicity of mRNA-1010 candidate seasonal influenza vaccine.

Summary of Changes in Protocol Amendment 2:

Section # and Name	Description of Change	Brief Rationale
	Moved from exploratory to secondary objectives (Part B):	
	• To evaluate the immunological response of mRNA-1010 (for superiority) relative to a licensed SD seasonal influenza vaccine (Fluarix Quadrivalent) against vaccine-matched influenza A and B strains at Day 29.	
	• To further evaluate the humoral immunogenicity of each study arm against vaccine-matched influenza A and B strains at Day 29.	
Sections 3.3.1 and 4.3.1 (Overall Design): Table 9 (Part B), and Table 13 (Part C)	Amount of mRNA/Antigen for treatment group 3 (Table 9) and treatment group 5 (Table 13) changed from 50 µg to 12.5 µg, and for treatment group 6 (Table 13) from 15 µg to 60 µg.	To correct an error in dose calculation of mRNA/antigen.
Section 3.3.2 (Scientific Rationale for Study Design, Part B)	Updated scientific rationale for study design in Part B.	To align with updated objectives and endpoints.
Section 3.9.2 (Statistical Hypothesis), and Section 3.9.3 (Sample Size Determination, Part B)	Statistical hypothesis and the sample size determination were updated in Part B.	To align with the needed analyses for updated endpoints
Section 3.9.7 (Multiplicity, Part B)	Multiplicity adjustment criteria were updated. Figure 1 was moved from Section 4.9.7 to Section 3.9.7.	To align with testing noninferiority and superiority hypotheses in Part B.
Section 3.4.2 (Exclusion Criteria, Part B) and Section 4.4.2 (Exclusion Criteria, Part C)	Updated the exclusion criteria # 10 in Part B and Part C of the study.	To provide clarity on heart muscle inflammation exclusion in Parts B and C.

TABLE OF CONTENTS

CLINICAL	STUDY PROTOCOL	1
DECLARA	TION OF INVESTIGATOR	2
PROTOCO	L AMENDMENT SUMMARY OF CHANGES	3
LIST OF A	BBREVIATIONS AND DEFINITION OF TERMS	.15
1.	INTRODUCTION	.17
1.1.	Study Rationale	.17
1.2.	Background	.18
1.3.	Benefit/Risk Assessment	.18
1.3.1.	Risk Assessment	.18
1.3.2.	Benefit Assessment	.19
1.3.3.	Overall Benefit/Risk Conclusion	.19
2.	PART A	.20

Table 5:	Respiratory and Systemic Symptoms for Protocol-defined Influenza-like Illness	51
Table 6:	Populations for Analysis	54
Table 7:	Schedule of Activities (Part B)	61
Table 8:	Objectives and Endpoints (Part B)	64
Table 9:	Treatment Groups and Dose Levels (Part B)	65
Table 10:	Study Intervention(s) Administered	70
Table 11:	Schedule of Activities (Part C)	83
Table 12:	Objectives and Endpoints (Part C)	86
Table 13:	Treatment Groups and Dose Levels (Part C)	87
Table 14:	Study Intervention(s) Administered	92
Table 15:	Protocol-required Safety Laboratory Tests	106
Table 16:	Adult and Adolescent Solicited Adverse Reactions and Grades	110
Table 17:	Adverse Events of Special Interest	113
Table 18:	Case Definitions of Probably and Confirmed Myocarditis, Pericarditis, and Myopericarditis	114

LIST OF FIGURES

Figure 1:	Prespecified	Order for S	Superiority	Hypothesis	Testing.	79
-----------	--------------	-------------	-------------	------------	----------	----

LIST OF ABBREVIATIONS AND DEFINITION OF TERMS

The following abbreviations and terms are used in this study protocol.

Abbreviation or Specialist Term	Definition
AE	Adverse event
AESI	Adverse event of special interest
AFAB	Assigned female at birth
ANCOVA	Analysis of covariance
AR	Adverse reaction
CDC	Centers for Disease Control and Prevention
CEAC	Cardiac Event Adjudication Committee
CFR	Code of Federal Regulations
CI	Confidence interval
COVID-19	Coronavirus disease 2019
CRO	Contract research organization
CSR	Clinical study report
DHHS	Department of Health and Human Services
eCRF	Electronic case report form
EDC	Electronic data capture
eDiary	Electronic diary
EoS	End of study
FAS	Full Analysis Set
FDA	Food and Drug Administration
FSH	Follicle-stimulating hormone
GCP	Good Clinical Practice
GLSM	Geometric least square mean
GMFR	Geometric mean fold rise
GMR	Geometric mean ratio
GMT	Geometric mean titer
НА	Hemagglutinin
HAI	Hemagglutination inhibition
НСР	Healthcare practitioner
HD	High dose
HIV	Human immunodeficiency virus

Abbreviation or Specialist Term	Definition			
HRT	Hormonal replacement therapy			
IB	Investigator's brochure			
ICF	Informed consent form			
ICH	International Council for Harmonisation of Technical Requirements for Pharmaceuticals for Human Use			
ILI	Influenza-like illness			
IM	Intramuscular(ly)			
IND	Investigational new drug			
IRB	Institutional Review Board			
IRT	Interactive response technology			
IST	Internal safety team			
LNP	Lipid nanoparticle			
LTFU	Lost to follow-up			
MAAE	Medically attended adverse event			
MedDRA	Medical Dictionary for Regulatory Activities			
(m)RNA	(Messenger) ribonucleic acid			
NH	Northern Hemisphere			
NP	Nasopharyngeal			
POCBP	Person of childbearing potential			
PONCBP	Person of nonchildbearing potential			
РР	Per-protocol			
QTLs	Quality tolerance limits			
RNA	Ribonucleic acid			
RT-PCR	Reverse transcription polymerase chain reaction			
SAE	Serious adverse event			
SAP	Statistical analysis plan			
SCR	Seroconversion rate			
SD	Standard dose			
SH	Southern Hemisphere			
SoA	Schedule of Activities			
WHO	World Health Organization			

1. INTRODUCTION

Seasonal influenza viruses are estimated by the WHO to cause 3 to 5 million cases of severe illness and up to 650,000 deaths each year, which is a severe challenge to public health (WHO 2023). Influenza epidemics occur each year and follow a seasonal circulation pattern with increased cases during the winter months in the NH and SH, respectively (Riedel et al 2019). Since influenza viruses continuously change through a process termed antigenic drift, the circulating viruses are actively monitored by a worldwide monitoring network coordinated by the WHO (Monto 2018). Based on the observed circulation patterns and antigenic changes, an expert panel recommends influenza virus strains to be used for vaccine manufacturing twice a year (once for the NH and once for the SH). Influenza A and B viruses are the most relevant influenza A H1N1 strain, 1 influenza A H3N2 strain, and 2 influenza B strains (covering the B/Victoria and B/Yamagata lineages) (WHO 2023a, WHO 2023b).

Currently licensed seasonal influenza virus vaccines rarely exceed 60% overall effectiveness and are poorly effective during the years when circulating viruses do not match the strains selected for the vaccine antigens (CDC 2023a). Influenza vaccines based on mRNA technology could provide several benefits compared with current vaccines, including the ability to respond to strain changes more quickly, avoidance of mutations that may be acquired during vaccine production in eggs or cell culture, stronger immune responses, and improved protection in older adults (Rockman et al 2020).

The Sponsor has developed a rapid response proprietary vaccine platform based on an mRNA delivery system. The platform is based on the principle and observations that cells in vivo can take up mRNA, translate it, and then express protein viral antigens(s) on the cell surface. The delivered mRNA does not enter the cellular nucleus or interact with the genome, is nonreplicating, and is expressed transiently.

ModernaTX, Inc. (the Sponsor) is using its mRNA-based platform to develop an LNP-encapsulated mRNA-based vaccine against disease caused by influenza virus types A and B. The proposed development candidate, mRNA-1010, is a quadrivalent vaccine containing mRNAs that encode for the HA of the 4 strains recommended by the WHO for cell or recombinant-based vaccines. Equal amounts of mRNAs encoding for each of the 4 different strains will be used for the HA components. The mRNA-1010 development candidate is administered as a single IM injection and aims to elicit protection from all seasonal influenza viruses covered by the vaccine.

1.1. Study Rationale

The Sponsor is conducting this Phase 3 study (mRNA-1010-P303) of its seasonal influenza mRNA vaccine (mRNA-1010) in 3 parts (Part A, Part B, and Part C), to establish immunogenicity and safety in support of licensure. The design of this study will include immunogenicity objectives for HAI, a surrogate endpoint of prevention of influenza illness and its complications. The rationale for this approach is based on the established precedent of using HA-based immunologic correlates for clinical assessment and licensure of influenza vaccines (DHHS 2007a, DHHS 2007b, Dunning et al 2016, European Medicines Agency 2016). The Sponsor has optimized mRNA-1010, previously studied, to **CCL**

1.2. Background

mRNA-1010 is an LNP-encapsulated, mRNA-based, prophylactic vaccine containing 4 mRNAs in an equivalent mRNA mass ratio that encode membrane-bound HA of the 4 different influenza strains, recommended by the WHO for 2022 to 2023 (Part A) and 2023 to 2024 (Parts B, and C) NH cell or recombinant-based vaccines.

The Sponsor has completed a Phase 1/2 study of mRNA-1010 (mRNA-1010-P101, NCT04956575) at dose levels up to 200 µg and is now conducting two Phase 3 studies at a 50-µg dose level: mRNA-1010-P301, a safety and immunogenicity study (NCT05415462) and mRNA-1010-P302, a safety and efficacy study (NCT05566639).

Data from study mRNA-1010-P101 Phase 2 NH suggest an improved and more durable immune response against influenza A strains compared to a licensed seasonal influenza vaccine at Day 29, Day 91, and Day 181. No safety concerns were identified. The 50-µg dose was chosen for the Phase 3 studies based on the observed reactogenicity and immunogenicity profile. Interim results at Day 29 from the Phase 3 mRNA-1010-P301 study indicate no safety concerns. Compared to licensed influenza vaccine, mRNA-1010 achieved superiority on seroconversion rates for A/H3N2 and A/H1N1, as well as superiority on geometric mean titer ratios for A/H3N2 and non-inferiority on geometric mean titer ratios for A/H1N1. Noninferiority was not met for either endpoint for the influenza B/Victoria- and B/Yamagata-lineage strains. In order to improve the immune response to the influenza B strains, the Sponsor has since optimized mRNA-1010 (see Section 1.1).

Additional details of mRNA-1010 are provided in the IB.

1.3. Benefit/Risk Assessment

1.3.1. Risk Assessment

There have been very rare (<1 in 10,000 recipients) reports of myocarditis and pericarditis occurring after vaccination with COVID-19 vaccines, including mRNA vaccines. The majority of the cases have been reported in adolescent and young adult persons assigned male at birth shortly after the second dose of the vaccine. These are typically mild cases and individuals tend to recover within a short time following standard treatment and rest (Gargano et al 2021). Investigators and participants should be alert to the signs and symptoms of myocarditis and pericarditis (see Section 5.5). The risk of myocarditis or pericarditis after administration of non-coronavirus disease mRNA vaccines is unknown.

Safety and reactogenicity data from a Phase 1/2 study of mRNA-1010 (mRNA-1010-P101, NCT04956575) with dose levels up to 200 µg revealed no safety concerns. Additional details are provided in the IB.

1.3.2. Benefit Assessment

Participants will obtain information about their general health status through the medical evaluations/assessments associated with this study (ie, physical examination, vital signs measurement).

Participants will be contributing to the process of developing a new potentially prophylactic measure for influenza infection.

1.3.3. Overall Benefit/Risk Conclusion

Considering the safety data for mRNA-1010 to date, the Sponsor considers the potential benefits of participation to exceed the risks.

2. PART A

2.1. **Protocol Summary**

2.1.1. Synopsis (Part A)

Protocol Title: A Phase 3, randomized, stratified, observer-blind, active-controlled study to evaluate the immunogenicity, reactogenicity, and safety of mRNA-1010 seasonal influenza vaccine in adults 18 years and older

Brief Title: A Phase 3 study to evaluate the immunogenicity and safety of mRNA-1010 candidate seasonal influenza vaccine in adults.

Regulatory Agency Identifier Number(s):

Registry	ID
FDA	IND 27460

Rationale:

The Sponsor is conducting Part A of this Phase 3 study of its candidate seasonal influenza mRNA vaccine (mRNA-1010), mRNA-1010-P303, to establish immunogenicity and safety in support of licensure. The design of this study will include immunogenicity objectives for HAI, a surrogate endpoint of prevention of influenza illness and its complications. The rationale for this approach is based on the established precedent of using HA-based immunologic correlates for clinical assessment and licensure of influenza vaccines (DHHS 2007a, DHHS 2007b, Dunning et al 2016, European Medicines Agency 2016). The Sponsor has optimized mRNA-1010, previously studied in 2 previous Phase 3 trials, CCL

Objectives and Endpoints:

Objectives	Endpoints			
Primary				
• To evaluate the humoral immunogenicity of mRNA-1010 relative to that of a licensed active comparator (Fluarix [®] Quadrivalent) against 4 vaccine-matched influenza virus A and B strains at Day 29.	 GMT at Day 29 as measured by HAI. Proportion of participants reaching seroconversion at Day 29 as measured by HAI. 			
To evaluate the reactogenicity and safety of mRNA-1010.	 Solicited local and systemic ARs through 7 days after study intervention dosing. Unsolicited AEs through 28 days after study intervention dosing. MAAEs from Day 1 to Day 181/EoS. AESI from Day 1 to Day 181/EoS. SAEs from Day 1 to Day 181/EoS. AEs leading to discontinuation from study participation from Day 1 to Day 181/EoS. 			

	Objectives	Endpoints
Se	condary	
•	To further evaluate the humoral immunogenicity of mRNA-1010 against 4 vaccine-matched influenza virus A and B strains at Day 29.	 The proportion of participants with HAI titer ≥1:40 at Day 29. GMFR comparing Day 29 to Day 1 (Baseline) as measured by HAI.
Ex	ploratory (May be Performed)	
•	To evaluate the humoral immunogenicity of mRNA-1010 relative to that of a licensed active comparator (Fluarix Quadrivalent) against 4 vaccine-matched influenza virus A and B strains at Day 181/EoS.	 GMT at Day 181 as measured by HAI. Proportion of participants reaching seroconversion at Day 181 as measured by HAI.
•	To evaluate the humoral immunogenicity of mRNA-1010 relative to that of a licensed active comparator against vaccine-matched or vaccine- mismatched A and B strains, including the use of alternative methods.	 GMT and GMFR of nAbs by assays such as MN assays or alternative methods against vaccine-matched or vaccine-mismatched strains on Day 29 compared with Day 1 (Baseline). GMT and GMFR of anti-HA antibodies as measured by HAI against vaccine-mismatched strains on Day 29 compared with Day 1 (Baseline).
•	To assess the occurrence of clinical influenza in study participants and characterize their immune response to infection and viral isolates.	• Frequency of RT-PCR-confirmed ILI and assessment of immune responses in participants with RT-PCR-confirmed ILI.

Abbreviations: AE = adverse event; AESI = adverse events of special interest; AR = adverse reactions; EoS = end of study; GMFR = geometric mean fold rise; GMT = geometric mean titer; HA = hemagglutinin;

HAI = hemagglutination inhibition; ILI = influenza-like illness; MN = microneutralization; MAAE = medically attended adverse event; mRNA = messenger ribonucleic acid; nAb=neutralizing antibody; RT-PCR = reverse transcription polymerase chain reaction; SAE = serious adverse event.

Overall Design Synopsis:

mRNA-1010-P303 Part A is a Phase 3, randomized, stratified, observer-blind, active-controlled study to evaluate the immunogenicity, reactogenicity, and safety of mRNA-1010 seasonal influenza vaccine in adults 18 years and older.

Approximately 2400 medically stable adults at least 18 years of age inclusive, at the time of signing the ICF will be randomly assigned to treatment in this study in a 1:1: ratio to 1 of 2 treatment groups to receive either a single dose of mRNA-1010 or a single dose of a licensed seasonal influenza vaccine as an active comparator (Fluarix Quadrivalent) at Day 1. Randomization will be stratified by age categories (18 to <50 years old, \geq 50 to <65 years old, or \geq 65 years old) and influenza vaccine status in the prior 12 months (received or not received).

Brief Summary:

The study aims to demonstrate noninferiority of mRNA-1010 versus a licensed quadrivalent seasonal influenza vaccine (an active comparator) in the immune response, as measured by GMT and by seroconversion rate at Day 29, using HAI assay, for each of the 4 vaccine-matched influenza virus A and B strains.

Study details include:

- There will be 4 clinic/in-person visits (Screening Visit and at Days 1, 29 and Day 181 (Month 6)/EoS) and 2 safety phone calls at Days 8 and 91 as specified in the SoA. The Screening Visit and Day 1 may be performed on the same day or a different day.
- All participants will be asked to complete an eDiary for solicited ARs for 7 days (ie, the day of study intervention dosing and 6 subsequent days).
- Detection of all AEs will be through 28 days after study intervention dosing (ie, the day of study intervention dosing and 27 subsequent days). Detecting MAAEs, AESI, SAEs, and AEs leading to discontinuation from study participation will continue through Day 181 (Month 6)/EoS.

Number of Participants: Approximately 2400 participants will be enrolled in Part A.

Study Arms and Duration:

- The study will comprise 2 study arms: investigational vaccine (mRNA-1010) group and active comparator (a licensed quadrivalent seasonal influenza vaccine) group.
- The total study duration (including Screening) for each participant is up to 7 months.

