2.1.2. SoA (Part A)

Table 1:Schedule of Activities (Part A)

Visit Number		1	2	3	4	5	USV	Notes
Type of Visit	С	С	SC	С	SC	С	С	
Month Timepoint				M1	M3	M6	Up to M6	
Visit Day	Screening ^a	D1 (Baseline)	D8	D29	D91	D181/ EoS	N/A	
Window Allowance (Days)	-28	N/A	+3	-7 to +3	±5	±14	N/A	
Informed consent form, demographics, concomitant medications, medical history ^b	X							
Inclusion/exclusion criteria	X	Х						Refer to Section 2.4.1 and Section 2.4.2
Physical examination ^b	X							Refer to Section 2.8.3.1
Vital signs measurements	Х	Х						Refer to Section 2.8.3.2
Pregnancy testing	X	Х						Prior to study intervention dosing on Day 1 Refer to Section 2.8.3.3
Randomization		Х						Refer to Section 2.6
Blood collection for future research sample (optional)		Х						Prior to study intervention dosing Refer to Section 2.8.6 and Section 5.1.3
Blood collection for transcriptomics (optional)		Х		X				Prior to study intervention dosing on Day 1 Refer to Section 2.8.7

Visit Number		1	2	3	4	5	USV	Notes
Type of Visit	С	С	SC	С	SC	С	С	
Month Timepoint				M1	M3	M6	Up to M6	
Visit Day	Screening ^a	D1 (Baseline)	D8	D29	D91	D181/ EoS	N/A	
Window Allowance (Days)	-28	N/A	+3	-7 to +3	±5	±14	N/A	
Study intervention dosing (including 30-minute,		Х						One IM injection in the deltoid muscle
postdose observation period) ^c								Refer to Section 2.5.2.2
Blood collection for humoral immunogenicity		Х		Х		Х		Prior to study intervention dosing on Day 1
NP swab for virus detection ^d		Х					X	Prior to study intervention dosing on Day 1 Refer to Section 2.8.3.4 and Section 2.8.3.11.3
eDiary activation for recording solicited ARs (7 days) ^e		Х						Refer to Section 2.8.3.6
Review of solicited ARs eDiary		Х	Х					
Follow up safety call ^f			Х		Х			Refer to Section 2.8.3.5
Recording of unsolicited AEs		Х	Х	X			X ^g	Refer to Section 2.8.3.8 and Section 5.3

Visit Number		1	2	3	4	5	USV	Notes
Type of Visit	С	С	SC	С	SC	С	С	
Month Timepoint				M1	M3	M6	Up to M6	
Visit Day	Screening ^a	D1 (Baseline)	D8	D29	D91	D181/ EoS	N/A	
Window Allowance (Days)	-28	N/A	+3	-7 to +3	±5	±14	N/A	
Recording of SAEs, AESIs, MAAEs, AEs leading to discontinuation from study participation, and concomitant medications/procedures relevant to or for their treatment ^h		Х	Х	X	х	х	X ^g	
Recording of concomitant medications ⁱ		Х	Х	X				Refer to Section 2.6.6.2
Recording of concomitant procedures/surgeries		Х	Х	X	Х	Х	Xg	Refer to Section 2.6.6.2
Recording of non-study vaccinations ^j		Х	Х	X	Х	Х		Refer to Section 2.6.6.2

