2.5.3. Immunogenicity Analysis

For immunogenicity analysis, antibody titers reported as below the LLOQ will be replaced by 0.5 x LLOQ. Values that are greater than the ULOQ will be converted to the ULOQ.

The primary analysis population for immunogenicity will be the PP Immunogenicity Set, unless otherwise specified. The primary objective of this study is to use the immunogenicity response to infer efficacy in participants receiving mRNA-1010, see Section 2.3.2 for statistical hypotheses.

Immune responses, as measured by GMT and seroconversion rate in the mRNA-1010 group based on Day 29 HAI titers, will be compared to that in participants receiving the active comparator for all 4 strains.

Rate of seroconversion is defined as the proportion of participants with either a pre-vaccination HAI titer <1:10 and a post-vaccination titer \geq 1:40 or a pre-vaccination HAI titer \geq 1:10 and a minimum 4-fold rise in post-vaccination HAI antibody titer.

The primary immunogenicity estimands are presented in detail in Table 17. The Day 29 primary analysis of immunogenicity will be performed after all participants have completed the Day 29 visit.

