CCI

Descriptive statistics (n, median, min, max) may be provided for GMT with corresponding 95% CI at each time point for participants with RT-PCR-confirmed protocol-defined ILI. Additionally, the number and percentage of participants with seroconversion at each time point may be provided with 2-sided 95% CI using the Clopper-Pearson method for participants with RT-PCR-confirmed protocol-defined ILI.

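### Part A: titres and seroconversion at fixed visits in confirmed influenza cases cannot separate the response to infection from the response to vaccine

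*Protocol*

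**What the plan says.** The Part A synopsis and Table 2 of the protocol (2.1.1, 2.2) list as an exploratory objective "To assess the occurrence of clinical influenza in study participants and characterize their immune response to infection and viral isolates". The endpoint attached to it is "Frequency of RT-PCR-confirmed ILI and assessment of immune responses in participants with RT-PCR-confirmed ILI". It names no reference time and no pre-infection baseline.

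SAP 2.5.3.5 defines a confirmed case. After a redacted block, it says that descriptive statistics "may be provided for GMT with corresponding 95% CI at each time point for participants with RT-PCR-confirmed protocol-defined ILI". It adds that "the number and percentage of participants with seroconversion at each time point may be provided with 2-sided 95% CI using the Clopper-Pearson method". Both are optional.

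The only definition of seroconversion is in SAP 2.5.3 (the same as protocol 2.9.5.1): "Rate of seroconversion is defined as the proportion of participants with either a pre-vaccination HAI titer <1:10 and a post-vaccination titer" of at least 1:40, or a 4-fold rise from a pre-vaccination titre of at least 1:10. The reference sample is therefore always Day 1.

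In the Part A schedule (protocol 2.1.2, Table 1), the row "Blood collection for humoral immunogenicity" is marked at Days 1, 29 and 181 and is blank for unscheduled visits. The ILI visit in protocol 2.8.3.4 consists of symptom assessment and a nasopharyngeal swab. The immunogenicity visit windows in SAP 7.3 count from injection.

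The PP Immunogenicity Set is the default for immunogenicity analyses. In Part A it excludes participants with confirmed influenza between Days 1 and 29 (protocol 2.9.4, SAP 2.4).

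**The concern.** The objective concerns what infection does to antibody. That needs a sample before the illness, a sample after it, and the change between them. The visible analysis instead compares each visit with Day 1, so the interval always includes the vaccination. A participant who seroconverted to the vaccine and had no further rise after influenza counts as seroconverted, exactly like one whose rise came from the infection.

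Results are presented by vaccination group (SAP 2.5.1). A difference between arms in vaccine response would therefore appear in this table and could be read as a difference in response to breakthrough infection. At stake is the meaning of one exploratory table.

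**Working it through.** **Where each sample falls relative to infection (default PP set).**

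- Day 1: before vaccination and before infection.
- Day 29: confirmed cases on Days 1 to 29 have been removed, so the remaining onsets come later and this sample essentially precedes infection. The exception is at the window edge. SAP 2.4 accepts a Day 29 sample from Day 22 to Day 43, so an onset on Days 30 to 43 may fall before or after that participant's own draw. Only actual dates settle it.
- Day 181: mostly after infection, but compared with Day 1. The change is vaccine response after waning, plus any infection response.

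**Day 29 seroconversion if infection raises no antibody.** Protocol 2.9.3 and SAP 2.3.3 assume 69% (A) and 59% (B) for mRNA-1010, 1 point below the comparator. These rates reproduce the stated seroconversion power. With 1020 per arm and a 10-point margin:

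- power = Φ((0.10 − 0.01)/SE − 1.96), SE = √[p₁(1−p₁)/1020 + p₂(1−p₂)/1020]
- A (0.69 v 0.70): 0.9930; B (0.59 v 0.60): 0.9854
- all four strains, treated as independent: 0.9930² × 0.9854² = 0.957 (plan: at least 95%)

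So the planned table would be expected to show about 69% and 59% at Day 29 in the mRNA-1010 arm with no infection response at all.

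**Day 181 seroconversion if infection raises no antibody.** The documents give no waning figure, so the following are assumptions: seroconversion taken as a 4-fold rise; log fold rise at Day 29 normal with SD s from 0.8 to 1.5, calibrated to 69% and 59%; a fraction k of 0.50 to 0.75 of the log rise retained at Day 181; no assay noise. Then

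SCR at Day 181 = Φ(z_p − ln 4 × (1/k − 1)/s), with z_p = 0.496 (A) and 0.228 (B).

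| | s = 0.8, k = 0.50 | s = 1.5, k = 0.75 |
|---|---|---|
| A | Φ(0.496 − 1.733) = 11% | Φ(0.496 − 0.308) = 57% |
| B | Φ(0.228 − 1.733) = 7% | Φ(0.228 − 0.308) = 47% |

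All of this is vaccine response.

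**The same assumptions with an infection-anchored measure (Day 181 over Day 29, onset in between).** The mean log rise at Day 29 is μ = ln 4 + s·z_p, and the geometric mean ratio is exp(−(1−k)μ) times any infection effect.

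- No infection effect: ratio 0.34 to 0.68; none show a 4-fold rise.
- A 4-fold infection effect still present at Day 181: ratio 1.38 to 2.70, which is 4 times the no-infection value in every setting (for example 1.64/0.41 = 4.0). Yet only 1% to 12% show a 4-fold rise from Day 29, because waning offsets part of it.

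The fold rise set against participants without confirmed influenza therefore recovers the infection effect. The 4-fold percentage alone would understate it.

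**The case against.** The strongest objection is the redaction. A blacked-out block stands inside the very bullet at issue, and it may already specify an onset-based or Day 181 against Day 29 comparison. This stands: the point holds for the visible text only. The block could not supply an illness-time or convalescent serum, since the unredacted schedule has none.

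A reader might also infer several stronger things that the documents do not support:

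- *The SAP reports vaccine response as response to infection.* No visible text labels it so. The endpoint and the SAP bullet speak of immune responses in participants with confirmed ILI; the link to infection comes from the objective.
- *Pre- and post-infection titres are averaged together.* In the default set this arises mainly at the window edges.
- *All four strains are used whatever the infecting virus.* The paragraph names no strain.
- *Day 181 seroconversion has a floor of 69% and 59%.* That assumes no waning.

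Side-by-side Day 29 and Day 181 GMTs would permit an informal before-and-after reading, but no such contrast is specified. Finally, the planning rates are for all vaccinees; breakthrough cases may have responded less to vaccine.

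**Conclusion.** The point holds in a limited form. On the visible text, the Part A measures for confirmed cases do not isolate the response to infection that the objective names. In the default set, Day 29 seroconversion is essentially vaccine response, about 69% (A) and 59% (B) under the plan's mRNA-1010 assumptions. Day 181 seroconversion mixes vaccine and infection response. With no infection response it would still be 11% to 57% (A) and 7% to 47% (B), under waning assumptions that are illustrative and not from the documents. If early infections are kept, as in the Immunogenicity Set, Day 29 is mixed as well.

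Severity is low. The objective is exploratory, the tables are optional, and no alpha, sample size, primary result or secondary result is affected.

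**What to change.** Unless the redacted text already does this, amend SAP 2.5.3.5 as follows.

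- For cases with ILI onset after the actual Day 29 draw and before the actual Day 181 draw, report by arm the GMFR and the percentage with a 4-fold or greater rise from the Day 29 to the Day 181 sample. Use actual onset and draw dates, not nominal visits.
- Show the same Day 29 to Day 181 change in participants without confirmed influenza as the reference for waning.
- Restrict to the HAI strain of the infecting type or subtype only where RT-PCR reports it; the visible text does not promise subtyping.
- Label titres drawn before onset as pre-infection titres. Show any cases with onset before the Day 29 draw separately, as confounded with vaccination.

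No new visit or blood draw is needed. Serum is already scheduled, and the case definition (RT-PCR within 7 days of onset) requires an onset date. The cost is SAP wording and modest programming.

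There are two drawbacks. Cells may be small. The addition would also come after the Part A primary results were known: Amendment 1 of 10 October 2023 reports them, and SAP version 2.0 is dated 3 April 2024. It should be recorded as an exploratory change made after that unblinding; protocol 2.9 provides for listing exploratory changes, with timing and reason, in the SAP or CSR.
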